The Canadian Occupational Performance Measure (COPM) is “an individualized outcome measure designed to assess clients’ perception of their occupational performance and satisfaction with that performance” (Donnelly, O’Neill, Bauer, & Letts, 2017). A systematic review (Parker & Sykes, 2006) found that this assessment allows clients to identify personal goals they would like to work on throughout their time in occupational therapy (Donnelly, O’Neill, Bauer, & Letts, 2017). It has also been used in research studies to measure change in perceived performance and satisfaction with performance (Plach, Sells, 2013).

The PTSD Checklist for DSM-5 (PCL-5) assesses the 20 DSM-5 symptoms of PTSD through a 20-item self-report measure. There are several purposes of the PCL-5, including: “monitoring symptom change during and after treatment, screening individuals for PTSD, and making a provisional PTSD diagnosis.” In the PCL-5, individuals are presented with a list of problems people may have as a result of

a stressful situation. Individuals are asked to indicate how much they have been bothered by this problem in the past month. Problems can be rated as “not at all, a little bit, moderately, quite a bit, or extremely” (Weathers et al., 2013). The PCL-5 demonstrates sound psychometric properties according to Wortmann et al. (2016).

The Depression Anxiety and Stress Scales (DASS) is a screening tool to assess symptoms of depression, anxiety, and stress in community settings (Tran, Tran, & Fisher, 2013). The DASS-21 asks 21 questions and is comprised of three subscales: The Depression sub-scale which measures hopelessness, low self-esteem, and low positive affect; the Anxiety scale which assesses autonomic arousal, musculoskeletal symptoms, situational anxiety and subjective experience of anxious arousal; and the Stress scale which assesses tension, agitation, and negative affect (Tran, Tran, & Fisher, 2013). The DASS-21 will also be used as a quantitative outcome measure pre and post-test to measure changes in mental health.

Discharge focus groups will be used to identify coping strategies after participating in occupational therapy intervention in combination with SCUBA or SCUBA diving alone. Therefore, individual focus groups will be held for the experimental and control groups. Qualitative information will provide in depth information about participants’ experiences with SCUBA diving and occupational therapy, and the impact on mental health and daily life.

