13. Participants in the **experimental group** will complete 3-week OT program for 1.5 hours each week. After 4 weeks total, a follow-up phone call will be given with general questions regarding experience with OT and SCUBA diving.

(See Appendix K for more details of research program)

Week 1	Week 2	Week 3	Week 4	Week 8
Informed consent Pre-test assessments Focus Group (audio will be recorded and transcribed)	OT Program Orientation Mindfulness strategies Journaling activity	OT Program Social community reflection Focus group to reflect on week 1 (audio will be recorded and transcribed) (See focus group questions in Appendix K)	OT Program Social community reflection Focus group to reflect on week 2 (audio will be recorded and transcribed) (See focus group questions in Appendix K)	Follow-up phone call after 4 weeks (audio recorded and transcribed) Discharge focus

		
Journaling activity
 
Trust-building activity
 
Total time: 1.5 hours
	
group (audio will be recorded and transcribed)
 
Journaling activity
 
Post-test assessments
 
Total time: 1.5 hours
	
--	--	---	---	--

14. Participants in **control group** will continue SCUBA diving without OT. They will participate in a discharge focus group discussion and complete post-test assessments. However, they will not receive a follow up phone call.

Week 1	Week 2	Week 3	Week 4
Informed consent	SCUBA dive without OT	SCUBA dive without OT	SCUBA dive without OT
Pre-test assessments			Post-test assessments

Focus Group (audio will be recorded and transcribed)
 
Total time: 1.5 hours
			
Discharge focus group (audio will be recorded and transcribed)
 
Total time: 1.5 hours

---	--	--	---

15. For post-test, have participants complete the COPM (Appendix F), PCL-5 (Appendix G), and DASS-21 (Appendix H).
16. The discharge focus group will be completed for both the experimental and control groups during week 4.
17. Complete field notes.
18. Transcribe focus groups within two weeks.
19. Complete follow up phone call after 4 weeks, for experimental group only, following the follow-up phone script (Appendix J).
20. Upload interviews to DeDoose for qualitative data analysis
21. Utilize SPSS to analyze quantitative data from COPM, PCL-5, and DASS-21

Risk and Injury

Breach of Confidentiality

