- Pseudonyms will be used to identify participants; a master list will document each participant's pseudonym. The master list will be stored separately to all data collected. All interviews will be transcribed by using headphones to ensure others will not hear the data. Data collected from focus groups, interviews and questionnaires will be stored electronically and in hard copy. Data

in hard copy will be kept in a locked file and electronic data will be password protected. Within two weeks of recording and following audit for correctness of transcriptions, the audio recordings will be destroyed.

Discomfort/vulnerability disclosing personal information

Some focus group or interview questions may be upsetting or uncomfortable for participants. Participants will be informed that they do not need to share any information that they wish not to with the group or that makes them uncomfortable. If the participants experience emotional discomfort at any time throughout the duration of the study, they may refuse to answer the question or withdraw from the study at any time.

Data Management Including Labeling & Storage Data

Subject/Data Confidentiality

- To protect the participants' identity, the researchers will assign pseudonyms and create a master list. The master list containing participant's legal names will be available only to the researchers. Electronic data will be stored in secure files on a password protected school shared server. The master list will be stored separately to collected data.
- All hard copy data will be stored in a locked file until the study is completed, in a secure office at Loma Linda University.
- Upon completion of the data collection, the data will be stored for a minimum of three years in a locked file in the school of Allied Health Professions at Loma Linda University. Three years post research data will be destroyed.

Data Analysis

- Qualitative data will include focus groups and interviews and these will be transcribed verbatim. Transcripts will be coded individually, and then together as a group. A codebook will be created and then categorized to organize emerging themes.
- Once the quantitative data is completed, it will be uploaded into a database in SPSS for analysis. Demographic information will be analyzed using descriptive analysis. Changes in COPM, PCL-5, and DASS-21 scores will be tested using paired samples t-tests. Further, differences between groups will be analyzed using independent samples t-tests.

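### Apart from refusing a question, the only exit offered to a distressed participant is full withdrawal, so the Week 4 t-tests rest on completers and would be biased if exits track worsening

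*Combined protocol and SAP*

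**What the plan says.** Under Risk and Injury, the paragraph on discomfort in disclosing personal information first says that participants need not share anything they would rather keep private. It then turns to distress arising at any stage of the trial, for which the stated options are these: "they may refuse to answer the question or withdraw from the study at any time". So two responses are offered, skipping the question or leaving the study.

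The schedules under Procedures steps 13 and 14, with step 15, place one repeat of the COPM, PCL-5 and DASS-21 in Week 4, in the same week as the discharge focus group (step 16: "The discharge focus group will be completed for both the experimental and control groups during week 4"). The later phone call goes to the experimental group only and is described under Instruments as a qualitative measure, so it cannot supply a missing score. No listed step offers the forms to someone who has stopped attending, or asks that the reason be recorded.

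Data Analysis gives two quantitative comparisons: "Changes in COPM, PCL-5, and DASS-21 scores will be tested using paired samples t-tests", and "differences between groups will be analyzed using independent samples t-tests". It names no analysis set, no rule for a missing Week 4 score and no sensitivity analysis.

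**The concern.** A paired t-test can use only people with both scores. An independent t-test, whether on change or on post-test scores, also needs the Week 4 value. Anyone who leaves before Week 4 therefore drops out of both comparisons.

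That is harmless if leaving has nothing to do with symptoms. Here the outcomes are PTSD, depression, anxiety and stress symptoms, and the plan itself names emotional discomfort as an occasion for leaving, so a link is plausible. If those who leave tend to be those who worsened, the remaining participants look better on average with no real change. Unequal loss between arms is also plausible, because the experimental schedule includes reflection focus groups that the control schedule lacks.

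With at most 15 per arm, a few such exits could create an apparent improvement or hide a real deterioration. As written, the trial would hold neither the leavers' scores nor their reasons, so it could not tell.

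**Working it through.** The plan states no power, alpha, effect size, SD or dropout rate, so it has no figure to reproduce. The check sizes the bias under stated assumptions.

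**Inputs**
- 15 per arm: the recruitment cap in Recruitment.
- Exits before Week 4: not given; 1, 2 or 3 of 15 assumed.
- Change scores: assumed normal, SD 1, true mean 0, oriented so that positive is worse.
- Test level: not given; two-sided 5% assumed, so false improvement should occur 2.5% of the time.

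**Bias if exactly the k worst leave.** The three largest expected values among 15 standard normal changes are 1.736, 1.248 and 0.948. Removing them lowers the completers' mean by their sum divided by (15 − k):
- k = 1: 1.736 / 14 = 0.124 SD
- k = 2: (1.736 + 1.248) / 13 = 2.984 / 13 = 0.230 SD
- k = 3: (2.984 + 0.948) / 12 = 3.932 / 12 = 0.328 SD

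**Bias if the k leavers are random among the seven worst.** The seven worst average about 0.81 SD, so the shift is k × 0.81 / (15 − k):
- k = 1: 0.81 / 14 = 0.058 SD
- k = 2: 1.62 / 13 = 0.125 SD
- k = 3: 2.43 / 12 = 0.203 SD

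**False-improvement rates by simulation, no true change.** The paired test is run as a one-sample t-test on completers' changes. The independent test compares changes, with exits in the experimental arm only. Repeat runs differ by less than one percentage point.

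| Exits of 15 | Paired, random among worst 7 | Paired, exact worst | Independent, random among worst 7 | Independent, exact worst |
|---|---|---|---|---|
| 0 | 2.5% | 2.5% | 2.5% | 2.5% |
| 1 | 3.8% | 8.0% | 3.3% | 5.8% |
| 2 | 5.6% | 17.0% | 4.7% | 10.0% |
| 3 | 8.7% | 28.6% | 6.9% | 15.4% |

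A third model, with leavers drawn from everyone who worsened, lies between these: for three exits, 13.7% on the paired test and 8.8% on the independent test.

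**Masking.** With a true mean worsening of 0.33 SD and the three worst gone, the completers' mean is 0.33 − 0.328 = 0.002 SD, that is, no visible change.

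**Cases without bias.** Random exits leave the false-improvement rate at 2.5%. If the three worst leave each arm, the between-group difference stays centred on zero, but each arm still shows a spurious improvement of about 0.33 SD and its paired test is positive in about 29% of trials. In that extreme case the independent test also runs above its level (4.8% in the direction of benefit), because trimming shrinks the observed spread.

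**The case against.** The strongest case against the point is that its mechanism is assumed. The paragraph concerns upsetting focus group or interview questions. Nothing in the documents ties that discomfort to a rising PCL-5 or DASS-21, or says that leavers would be those who worsened. A right to withdraw at any time is ordinary participant protection, and pre-test to post-test runs only from Week 1 to Week 4. The largest rates need exactly the worst changers to leave, and for the between-group test, which serves the stated aim of comparing two groups, the milder model gives only 3.3% to 6.9%. Consent pages and appendices are not shown and may contain withdrawal terms; the field notes in step 17 might record reasons. All of this stands, and it is why the result is given as a conditional range.

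A reader might infer more than the documents support:
- That leaving is the only response offered to distress. It is not: refusing a question and not sharing with the group both let a person stay and complete Week 4. Neither is a way to stop sessions while remaining in follow-up.
- That the plan says leavers are excluded. It does not; this follows from what the tests require and from the absence of a missing-score rule.
- That the OT comparison is biased whatever happens. It is not, if exits are random or alike in both arms.
- That safety monitoring or a referral list is missing. The pages where it might appear are not shown.

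Nor does the point justify a rule that improvement may be claimed only if it survives a worst-case fill, with each missing score set to the largest worsening seen in any completer. With a true 0.8 SD gain and 1, 2 or 3 purely random exits, that rule cuts the paired test's power from 79%, 76% and 71% to 47%, 16% and 4%.

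**Conclusion.** The point holds as a conditional weakness that is cheap to remove. What the text establishes is that there is no visible route between skipping a question and leaving the study, that outcomes are re-measured once, and that the t-tests will therefore rest on completers. That leavers would be those who worsened is an assumption, as are the 1 to 3 exits, normal changes and the two-sided 5% level.

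Under those assumptions the bias in an arm's mean change runs from 0.06 SD (one exit, milder selection) to 0.33 SD (three exits, strongest selection). The within-group tests are the more exposed, because they have no comparison arm to cancel the shift; the between-group test is affected only to the extent that exits differ between arms. The lower ends of the ranges are modest, and the upper ends should be read as bounds. Apart from bias, a fall from 15 to 12 per arm raises the difference detectable with 80% power from 1.06 to 1.20 SD, so recovering Week 4 scores is worthwhile even if exits are random.

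**What to change.** (a) Risk and Injury: offer three choices instead of two, namely refuse a question, stop sessions but still be offered the Week 4 forms, or withdraw completely.

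(b) Procedures step 15: for anyone in either arm who misses the Week 4 session and has not withdrawn completely, offer the three forms by phone or mail within 7 days. Log arm, date and reason (distress, other, not given).

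(c) Data Analysis: report by arm the number assigned, the number with both scores, and exits by reason. If scores are still missing, show a sensitivity analysis over a range of assumed changes for leavers. For example, with m missing of 15 and an assumed mean change d among them, the arm's mean change is [(15 − m) × completers' mean + m × d] / 15; tabulate this for several values of d. It should inform the reader and not act as a condition for claiming improvement.

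The cost is a small IRB and consent amendment, including use of the master list to reach people who stop attending, plus about 25 minutes per leaver (the time step 10 allows for the forms). For 1 to 3 leavers per arm that is 2 × 25 = 50 to 6 × 25 = 150 minutes in total. The drawback is that those few participants complete the forms in a different mode, which should be reported. Complete withdrawal stays available and those who choose it are not pursued, so some scores may still be missing.

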Official Title: Does an occupational therapy program enhance mental health outcomes for veterans who scuba dive

NCT Number: NCT03928392

Document Date: 10/14/2018

Study Protocol and Statistical Analysis Plan

METHODS

Study Design

For this study, we will be using a quasi-experimental design to compare the effectiveness of two groups: occupational therapy in combination with SCUBA diving in comparison to SCUBA diving alone. Data will be collected through semi-structured interviews and standardized assessments to assess the impact on psychosocial skills and occupational engagement.

Inclusion/Exclusion Criteria

SCUBA diver veterans who have participated in the WAVES Project for at least 3 months and have completed 3 open water dives. Participants must be proficient in written and verbal English. Veterans must be between 18-95 years of age.

Recruitment

Recruitment Method Info

We will recruit up to 15 participants in the control and experimental group for a total of 30 veterans from the WAVES Project facility. Purposeful and snowballing sampling methods will be applied to recruit participants via flyer. The flyer will be sent via email to the director of the WAVES project. The director will then forward the electronic flyer to their members via email or Facebook. Additionally, a meeting will be scheduled at the WAVES Project facility where the researchers will reach out to the veterans via a verbal recruitment script (see Appendix B) and a physical flyer (Appendix A). Those who are interested in participating will contact the researchers via email or phone and will be scheduled to

attend the first group meeting. At the group meeting the research project will be overviewed and the informed consent form will be provided.

Instruments & Data Collection

This study will include the following instruments: Intake Focus Group (Appendix D), Demographic Questionnaire (Appendix E), COPM (Appendix F), PCL-5 (Appendix G), DASS-21 (Appendix H), Discharge Focus Group (Appendix I) and Follow-Up Phone Script (Appendix J).

A Intake Focus Group consists of four sections and will be used to identify participants' experiences with SCUBA diving, impact of negative emotions on daily life and coping strategies. Focus groups will be held with those in the experimental group and control group separately..

The demographic questionnaire will obtain information about participants' age, gender, ethnicity, marital status, study and work commitments.

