Follow-up phone interviews will be held individually with each participant in the experimental group. The interview will consist of six questions and be used as a qualitative outcome measure to explore the effects of occupational therapy in combination with SCUBA diving and its impact on participants’ mental health and daily life.

Informed Consent Process

Veterans interested in the study will be scheduled to attend a group meeting. At the meeting, the research study will be briefly described and the informed consent document will be provided and reviewed. Those who are interested in participating will sign the consent form prior to completing pre-assessments. Those who are interested in participating will sign the consent form prior to completing pre-assessments.

Procedures

After receiving IRB approval, we will:

1. Email the flyer (see Appendix A) to the WAVES director and ask the director to send the flyer to members of the WAVES.
2. Schedule recruitment opportunities to present the flyer (see Appendix A) and verbal recruitment script (see Appendix B) at end of a *WAVES* session to recruit up to 30 *WAVES* veterans with mental health conditions. Provide signup sheet to sign up if interested.
3. Hand out flyers (with contact information i.e. phone number and email) to participants of *WAVES*.
4. Individuals interested may contact the research team via email and phone to sign up for the study.
5. Interested individuals will arrive at the group meeting at the scheduled time (the group meeting will last 1 ½ hours).
6. At the group meeting, provide a brief overview of the study and informed consent document, approximately 5 minutes.
7. Obtain written informed consent to participate in study, approximately 10 minutes.
8. Randomly assign participants into one of two groups before pre-testing: Experimental group or control group, approximately 10 minutes.

9. Provide further explanation about SCUBA, occupational therapy and the research program, approximately 10 minutes.
10. For pre-test questionnaires, have participants complete the COPM (Appendix F), PCL-5 (Appendix G), and DASS-21 (Appendix H). approximately 25 minutes.
11. The group will then split and focus groups (see Appendix K) will be held for the experimental and control groups, approximately 25 minutes.
12. Conclude the meeting and review the upcoming schedule (as described in the following), approximately 5 minutes.

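### The between-group t-test does not say whether it compares post-test or change scores; ANCOVA on the pre-test already collected would settle this and is usually more precise.

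*Combined protocol and SAP*

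**What the plan says.** Data Analysis gives two sentences on testing the scores. The first is within-group: "Changes in COPM, PCL-5, and DASS-21 scores will be tested using paired samples t-tests". The second is the only statement on comparing the arms: "Further, differences between groups will be analyzed using independent samples t-tests". No score is defined for it and no covariate is named.

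Two hints point towards change scores. The second sentence opens with a connective that follows a sentence on changes, and Instruments & Data Collection says "The DASS-21 will also be used as a quantitative outcome measure pre and post-test to measure changes in mental health". That remark covers one instrument and does not define a between-group test.

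Under Procedures, COPM, PCL-5 and DASS-21 are completed at pre-test (step 10) and at post-test (step 15) in both groups. Step 8 reads "Randomly assign participants into one of two groups before pre-testing". Step 9, also ahead of the questionnaires, is "Provide further explanation about SCUBA, occupational therapy and the research program". Study Design, however, states "we will be using a quasi-experimental design to compare the effectiveness of two groups".

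**The concern.** The question is a between-group contrast, so the paired tests cannot answer it and everything rests on one under-specified sentence. A t-test on week 4 scores and a t-test on change scores both fit that sentence, have different precision, and can give different answers on the same data. If the score is chosen after the data are seen, the nominal 5% error rate no longer holds. With at most 15 per arm, precision is also scarce, and the plan does not say that the pre-test will be used to gain any.

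A second point affects any use of the pre-test. Assignment and a further explanation of OT come before it. If participants know their group by then, which the text does not say, self-reported pre-test answers could shift, and the pre-test would not be a clean baseline.

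**Working it through.** **Inputs.** From the documents: up to 15 per group (Recruitment), and the same three instruments before and after in both arms (Procedures, steps 10 and 15). There is no stated power, alpha, effect size, SD or correlation, so there is no figure of the plan's own to reproduce. Assumed: two-sided 0.05, normal scores, equal pre and post SDs (set to 1), a common slope, 15 per arm with no loss, and pre-post correlation rho over a range.

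**Standard error of the group difference, n = 15 per arm**

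- Post-test t: sqrt(2/15) = 0.365, 28 df.
- Change t: sqrt(2(1 − rho) × 2/15), 28 df. At rho 0.5: 0.365.
- ANCOVA: sqrt((1 − rho²) × (2/15) × (1 + 1/26)), 27 df; the last factor is the small-sample cost of estimating the slope. At rho 0.5: sqrt(0.75 × 0.1333 × 1.0385) = 0.322.

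The 95% CI half-width is the t quantile times the SE. At rho 0.5 this is 2.048 × 0.365 = 0.75 for either t-test and 2.052 × 0.322 = 0.66 for ANCOVA. Power is from the noncentral t distribution.

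| rho | Power at 0.8 SD: post / change / ANCOVA | Power at 0.5 SD | CI half-width (SD) |
|---|---|---|---|
| 0.3 | 56 / 43 / 58% | 26 / 20 / 27% | 0.75 / 0.89 / 0.73 |
| 0.5 | 56 / 56 / 67% | 26 / 26 / 32% | 0.75 / 0.75 / 0.66 |
| 0.7 | 56 / 78 / 83% | 26 / 40 / 44% | 0.75 / 0.58 / 0.55 |

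At 0.8 SD and rho 0.8 the powers are 56 / 92 / 93%. At rho 0.1 ANCOVA has 55% against 56% for the post-test t.

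**Where ANCOVA has the smaller variance.** Against the post-test t: (1 − rho²) × 27/26 < 1, so rho > sqrt(1/27) = 0.19. Against the change t: (1 + rho) × 27/26 < 2, so rho < 52/27 − 1 = 0.93. At 10 per arm the factor is 17/16, and the limits become sqrt(1/17) = 0.24 and 32/17 − 1 = 0.88.

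**Effect of the unstated score.** Both t-tests were applied to the same simulated data (200,000 trials, 15 per arm).

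| rho | Disagree on significance, 0.8 SD | Disagree, 0.5 SD | No effect: at least one significant |
|---|---|---|---|
| 0.3 | 32% | 23% | 8.9% |
| 0.5 | 33% | 27% | 9.2% |
| 0.7 | 38% | 35% | 9.4% |

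ANCOVA gives the same group effect whether the outcome is the post-test or the change score, so it removes the choice.

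**Pre-test shift from known allocation.** Suppose the OT arm's pre-test is shifted by s and a fraction k of the shift remains at week 4, with no OT effect. The bias is ks for the post-test t, ks − s for the change t, and ks − rho × s for ANCOVA. With an assumed s = 0.3 SD and rho 0.3 / 0.5 / 0.7 (type I error from 100,000 simulated trials):

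| Shift at week 4 | Post-test t | Change t | ANCOVA |
|---|---|---|---|
| Gone (k = 0) | 0; 5% | −0.30; 10 / 12 / 18% | −0.09 / −0.15 / −0.21; 6 / 7 / 12% |
| Half (k = 0.5) | +0.15; 7% | −0.15; 6 / 7 / 8% | +0.06 / 0 / −0.06; 5 to 6% |
| Full (k = 1) | +0.30; 12% | 0; 5% | +0.21 / +0.15 / +0.09; 9 / 7 / 6% |

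For rho between 0 and 1, the ANCOVA bias always lies between the other two. A 0.3 SD reporting shift at week 4 alone biases all three by 0.30 SD. Type I error is then 12 / 12 / 12 to 13% for the post-test t, 10 / 12 / 18% for the change t and 13 / 15 / 19% for ANCOVA.

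**The case against.** The planned test is not wrong, and change scores are the more natural reading of Data Analysis; a few words naming the score would close the gap without ANCOVA. That is fair, but those words are absent, and fixing the score on either t-test leaves precision unused over most of the plausible range.

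The gain rests on figures the documents do not give. If change scores are meant, ANCOVA adds about 5 points of power at rho 0.7 and under 2 at rho 0.8. If post-test scores are meant, it adds about 2 points at rho 0.3. The gain of about 11 points over both appears only near rho 0.5. This stands, and it is why the benefit is described as usual rather than certain.

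Disagreement between two tests is harmful only if the choice follows the data, and nothing in the documents suggests that it would. True; the point of specifying the score is that readers need not take this on trust.

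Under a week 4 reporting shift ANCOVA has the highest type I error of the three, because it is the most precise around the same biased value. That also stands. It is a limit of unblinded self-report and not a reason to prefer a noisier test.

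The pre-test order concern is conditional, and the 0.3 SD shift is illustrative. Agreed on both counts.

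**Conclusion.** The concern holds. The plan leaves the between-group score undefined and uses no covariate, although the pre-test is collected in both arms. At 15 per arm ANCOVA has lower variance than both t-tests for rho of about 0.19 to 0.93; the largest gain over the better t-test is near rho 0.5, where variance falls by about 22% (0.75 × 27/26 = 0.779). Outside that range it loses very little. This is worth fixing as a gap in wording and a cheap improvement.

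The size depends on the assumed effect and correlation, on full recruitment and retention, and on random assignment. If the groups are not in fact randomised, ANCOVA and change-score analyses can estimate different effects, and ANCOVA does not remove confounding. The effect of assigning before the pre-test cannot be settled from the documents.

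**What to change.** 1. Reconcile the design label in Study Design with the random assignment in Procedures, step 8, because the preference for ANCOVA rests on randomisation.
2. Replace the last two sentences of Data Analysis with wording such as: *For each score, the OT effect is the group difference in the week 4 score from a linear model with group and the week 1 value of that score (ANCOVA), by assigned group, with estimate and 95% CI. Paired pre-post changes are descriptive and are not used to conclude on OT.*
3. Run the first meeting in the order of steps 6, 7, 10, 8, 9, 11, 12, and remove from step 8 the words placing assignment ahead of the pre-test. Consent then still precedes the pre-test, and the pre-test precedes assignment. If the order cannot change, report the unadjusted week 4 difference and the change-score difference beside the ANCOVA, and state that none of the three is protected against reporting shifts from known allocation.

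The cost is two sentences, one degree of freedom and a reordering: 5 + 10 + 10 + 10 + 25 + 25 + 5 = 90 minutes in either order, which fits the 1.5-hour meeting. SPSS, already named, can fit the model. The reordering does not protect the week 4 self-reports, and multiplicity across the scores is a separate matter.
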